### 5.1.5 Exposure

All study drug exposure data will be listed based on the Study Drug Administration eCRF.

For the Part A Core Study Phase, compliance will be calculated as:

Compliance =

number of complete study doses administered during Part A total expected study dosesduring Part A x 100

Unless otherwise noted, during the Part A Core Study Phase, the number of expected doses is the number of days during Part A.

For the Part B Long Term Extension Phase, compliance will be calculated as:

Compliance =

number of complete study doses administered  $\frac{during Part B prior to study discontinuation/completion}{total number of expected study doses during Part B} x 100$ 

> where the total number of expected study doses will be based on the time a subject is assigned to the twice weekly dosing schedule and the everythree-days dosing schedule during Part B.

For total on-study time, compliance will be calculated as:

#### Version 1.0

Compliance =

number of complete study doses administered prior to study discontinuation total number of expected study doses prior to study discontinuation x 100

> Compliance during Part A, Part B, and total on-study time will be listed by subject. Additionally, exposure and compliance will be summarized for Part A, Part B, and total time on study using descriptive statistics by randomized dose level and by cohort.

## 5.2 Safety Analysis

The primary objective of the study is to assess the safety and tolerability of APL-2. The safety analyses will be performed on the safety set.

## 5.2.1 Adverse Events

TEAEs are defined as those AEs that occur after Dosing on Day 1, or worsen in severity, and up to 30 days after the last dose of APL-2. For subjects who rollover to Part B long term extension phase, any AE recorded on the date of Visit 15 (start of dosing for the extension phase) will be included in Part A. Version 20.0 of MedDRA will be used to classify all AEs.

AEs will be considered treatment-emergent (TEAE) unless there is clear indication that the event occurred prior to first dose of study drug. AEs present prior to the first dose of study drug administration that increased in severity or relationship to study drug after the first dose of study drug and up to 30 days beyond the last dose of study drug will be classed as a TEAE. Events with missing or partial dates will be handled such that in the absence of contradictory information an AE is treatment emergent. So, for a missing start date (where stop date is after date of first dose) the date will be imputed as the date of first dose; for a missing stop date the date will be imputed as the last study date. If a partial date is recorded, the following convention will be used to assign the AE:

If a start date is missing the day information and month/year is the

same as first dose date then use first dose date, else '01' will be used for the day; if a start date is missing the month and the year is the same as first dose date then use first dose date, else January will be used for the start month.

• If a stop date is missing the day information and month/year is same as last study date then use last study date, else last day of the given month will be used for the stop day; if a stop date is missing the month and year is the same as last study date then use last study date, else December will be used for the stop month.

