## 4.5 Interim Analysis

One interim analysis is planned when all subjects enrolled in the study have completed Part A, the Core Study Phase (screening to day 336) or discontinued prior to Day 336. The interim analysis will present all planned tables, listings, and figures (TLF) listed in Appendix 8.1 for only the Part A Core Study Phase. The data will consist of:

- For subjects who rollover into the Part B Extension Phase, all data collected through the date of Visit 15 will be included. For occurrence data, such as Adverse Events and Concomitant Medications, records with a start date on or before the Visit 15 (which is considered the start of dosing date for the extension phase) will be included.
- For all subjects who do not rollover into the Part B extension Phase (i.e. who discontinue during the Part A Core Study Phase), all data will be included.

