## 2. INTRODUCTION

This Statistical Analysis Plan (SAP) is prepared to provide a more technical and detailed elaboration of the principal statistical features stated in the protocol. The SAP will ensure that the tables, listings, and figures that will be produced and statistical methods that will be used for the final analysis are complete and accurate and will allow valid conclusions to be drawn.

In the development of this final analysis SAP, the following study documents were used:

- Protocol Number (Version 1.0 Amendment 4), 17 Jan 2019
- Electronic Case Report Form (eCRF), extracted 18 Oct 2021
- Medical Coding Guidelines (Version 5.0), 10 Sep 2021

The study protocol consists of two study parts for analysis (details of the scheduled assessments of the study parts can be found in Section 3.3 of the SAP):

- Core Study Phase (Part A): the study period of the daily 270/280 mg or 360 mg APL-2 dose regimen.
- Long Term Extension Phase (Part B): the study period of the twice or three times weekly 1080 mg APL-2 dose regimen.

Statistical Analysis Plan Version 1.0 was used for the production of the Interim Part A Core Study Phase Analysis. This SAP will present the results for the final analysis for subjects who rolled over into Part B, presenting the safety and efficacy results of Part B and Part A + B as whole completed study as well. Definitions for the study days and baselines are outlined in Section 4. Details of the planned analyses are outlined in Section 5.

In the event that a discrepancy is found between the descriptions in the statistical section of the protocol and this document, the description in this document supersedes the descriptions in the statistical section of the protocol. Any deviations from the final analysis plan or from what is outlined in the protocol will be discussed in the final study report.

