#### Part B: Long-Term Extension Phase:

Following Visit 15 (Week 48), subjects who elect to continue in the Part B Long-Term Extension Phase will return to the site at 12-week intervals indefinitely until the subject discontinues or the development program is terminated.

Specific procedures for each visit are listed in the Study Flow Chart for the Long-Term Extension Phase in Table 2 in Section 3.3.2.

At Visit 15 (Week 48), subjects electing to enter the Part B Long-Term Extension Phase will begin an APL-2 dose regimen of APL-2 1,080 mg twice weekly (with potential to escalate to APL-2 1,080 mg every 3 days). When switching from the Part A Core Study Phase formulation and dose of APL-2 (270 mg/d or 360 mg/d) to the formulation and dose intended for use in the Long-Term Extension Phase (APL-2 1,080 mg twice weekly), subjects should return to the site for APL-2 administration training and to conduct Dose Transition Visits 1, 2 and 4 weeks after the new dose is initiated and perform the procedures outlined in Appendix Section 8.1.

Subjects who plan on continuing in the Part B Long-Term Extension Phase should be instructed to skip their daily Part A Core Study Phase Dose the day prior to Visit 15 (i.e., the subject should not self-administer APL-2 on Day 335).

**Note:** The first dose of APL-2 1,080 mg should be administered at the Visit 15 (Day 336), with Dose Transition Visits at Week 49, Week 50, and Week 52. Some subjects may enter the Part B Long-Term Extension Phase prior to the availability of the sorbitol formulation. These subjects should continue on their Part A Core Study Phase dose into the Part B Long-Term Extension Phase. These subjects will transition to the Long-Term Extension Phase dose at the next scheduled visit at which the sorbitol formulation and dose is available, and should schedule Visits T1, T2, and T3 1, 2 and 4 weeks following the visit at which the sorbitol dose is initiated. These subjects should be instructed to skip their Part A dose the day before the visit at which the APL-2 1,080 mg twice weekly dose regimen is scheduled to be initiated.

Subjects who discontinue treatment early should complete one Early Termination Follow-up Visit (ETFU) 6 weeks after discontinuation of treatment, and one Early Termination (ET) Exit Visit 6 weeks after the ETFU as outlined in Appendix 8.1.

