#### 4.4.1 Safety Data

Where appropriate, screening values may be used as baseline in the event of missing or unusable Day 1 measurements. No imputation of missing data for early terminations will be performed.

However, both partial and completely missing dates/times that are not related to early terminations, in addition to missing safety data (e.g., missing severities) will be reviewed on a case-by-case basis for potential imputations. As a general rule, a conservative approach will be adopted as outlined in Section 5.2.1 (e.g. partial Adverse Event (AE) onset dates and missing severities will be taken as the earliest 'on treatment' start date and highest severity, respectively, consistent with the partial information available). Moreover, the original data, without imputations, will be presented separately in data listings.

For safety lab parameters that are below or above the limit of quantification, the data will be presented as-is in the listings, but the limit of quantification will be used for the purposes of calculating change from baseline.

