#### Version 1.0

#### 5.2.1 Adverse Events

#### 5.2.1.1 Treatment-Emergent Adverse Events (TEAE)

TEAEs are defined as those AEs that occur after Dosing on Day 1, or worsen in severity, and up to 8 weeks (56 days) after the last dose of APL-2.

AEs will be considered Treatment-Emergent (TEAE) unless there is clear indication that the event occurred prior to first dose of study drug. AEs present prior to the first dose of study drug administration that increased in severity or relationship to study drug after the first dose of study drug and up to 56 days beyond the last dose of study drug will be classed as a TEAE. Events with missing or partial dates will be handled such that in the absence of contradictory information an AE is Treatment-Emergent. So, for a missing start date (where stop date is after date of first dose) the date will be imputed as the date of first dose; for a missing stop date the date will be imputed as the last study date. If a partial date is recorded, the following convention will be used to assign the AE:

- If a start date is missing the day information and month/year is the same as first dose date then use first dose date, else '01' will be used for the day; if a start date is missing the month and the year is the same as first dose date then use first dose date, else January will be used for the start month.
- If a stop date is missing the day information and month/year is same as last study date then use last study date, else last day of the given month will be used for the stop day; if a stop date is missing the month and year is the same as last study date then use last study date, else December will be used for the stop month.

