#### 5.2.1.2 Treatment-Emergent Adverse Event Study Part

TEAE will be summarized by study part in Safety Set using the following definitions:

• Part A + B: will include all TEAE from a start date on or after the first dose of APL-2 in Part A up to 8 weeks (56 days) after the last

dose of APL-2 in Part B.

• Part B: will include all TEAE during Part B which is any AE with a start date on or after the date of first 1080 mg APL-2 dose up to the end of 8 weeks (56 days) after the last dose of APL-2 in Part B.

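### The Part B SAP anchors missing and partial AE start dates only to the first APL-2 dose, so post-switch events can drop out of Part B; separately, the two SAPs place switch-day AEs in different parts

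*SAP*

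**What the plan says.** There are two plans: the Part A SAP (April 2020) and the Part B SAP (November 2022). Section 2 of the Part B SAP explains their roles: "Statistical Analysis Plan Version 1.0 was used for the production of the Interim Part A Core Study Phase Analysis". The Part B SAP covers the final results for Part B and for Part A + B.

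**Switch day.** For subjects who roll over, Part A SAP section 5.2.1 says that "any AE recorded on the date of Visit 15 (start of dosing for the extension phase) will be included in Part A". Section 4.5 cuts the interim data in the same way, keeping "records with a start date on or before the Visit 15 (which is considered the start of dosing date for the extension phase". Part B SAP section 5.2.1.2 defines a Part B TEAE as "any AE with a start date on or after the date of first 1080 mg APL-2 dose". Both SAPs plan the switch for Visit 15 (Study Design, Part B): "The first dose of APL-2 1,080 mg should be administered at the Visit 15 (Day 336". Subjects who reach Visit 15 before the new formulation is available are the exception: "These subjects should continue on their Part A Core Study Phase dose into the Part B Long-Term Extension Phase".

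**Missing and partial start dates.** Part B SAP section 5.2.1.1 uses the date of first dose when the whole start date is missing and the stop date is later than that dose. When the day is missing, it uses the first dose date if month and year match it, and otherwise the 1st of the month. When the month is missing, it uses the first dose date if the year matches, "else January will be used for the start month". The section speaks of the first dose of study drug and never of the first 1080 mg dose. Section 4.4.1 gives the general principle, "partial Adverse Event (AE) onset dates and missing severities will be taken as the earliest 'on treatment' start date", and promises case-by-case review.

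**The concern.** The imputation rule was written to answer one question: is the event treatment-emergent? Pulling an uncertain date back to the first APL-2 dose, or to the start of the month or year, answers that safely. The Part B SAP then uses the same imputed date for a second question: did the event start before or after the change of regimen? For that purpose an early date is not neutral. It takes an event that may have begun on the 1080 mg regimen and places it on the earlier daily regimen.

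What is at stake is the Part B safety profile: the Part B columns of the AE tables and the Part B exposure-adjusted incidence (EAI, section 5.2.1.4). These are the displays a reader would use to judge tolerability of the 1080 mg regimen. The switch-day mismatch is a smaller matter. The same event can be reported under the daily regimen in the interim report and under the 1080 mg regimen in the final one.

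**Working it through.** The plan has no numerical figure to reproduce, because the study is descriptive. The check applies the stated rules to dates.

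**1. Switch day, with the first 1080 mg dose at Visit 15.**
- Part A rule: start date ≤ Visit 15 date. True for an AE on that date.
- Part B rule: start date ≥ first 1080 mg date. Also true.

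The AE is in the Part A report and in the Part B column of the final report. Both rules compare dates only, so an AE before that day's infusion and one after it are treated alike.

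**2. Worked example for imputation.** Assume a first APL-2 dose on 15 March 2018. Day 336 is 335 days later, 13 February 2019, and is taken as the switch. The AE truly began after the switch.

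| Start date recorded | Imputed to | Part B Study Day | In Part B? |
|---|---|---|---|
| Day missing (February 2019) | 1 February 2019 | −12 | No |
| Month missing (2019) | 1 January 2019 | −43 | No |
| Fully missing | 15 March 2018 | −335 | No |

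**3. All first-dose dates in one year.** Assume each of the 365 first-dose dates of 2018, with the switch at Day 336.
- Day missing, true onset on or after the switch within the switch month: 5,738 date combinations, of which 5,373 fall out of Part B (5,373 / 5,738 = 93.6%). The other 365 are kept only because the switch is on the 1st (12 of 365 switch dates).
- Month missing, true onset from the switch to year end: 66,430 of 66,795 fall out (99.5%). The other 365 belong to the single switch date of 1 January.
- Day missing, true onset before the switch within the switch month: 0 of 5,373 combinations are wrongly moved into Part B.

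The error runs one way. These percentages are shares of possible dates, not expected shares of events.

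**4. Effect on the Part B EAI.** The plan's formula is e = n × 100 / EY, where n is the number of subjects with the event and EY is the sum of times to onset in years. A subject without the event contributes time up to last dose + 56 days. Suppose k subjects have the event and one loses their only occurrence. Then n becomes k − 1, and that subject's time lengthens or at least does not shorten. The new rate is at most (k − 1)/k of the old one: zero for k = 1, at most 50% for k = 2, at most 75% for k = 4. If the subject has a later dated occurrence, n is unchanged and only the time to onset lengthens.

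**5. Effect on a Part B percentage.** One reassigned subject changes a row by 100/N points, where N is the number in that cohort's Part B set, and only if the subject has no other qualifying Part B event in that row. N is not given. Assuming N = 12 (the cohort target) gives 100/12 = 8.3 points; assuming N = 6 gives 100/6 = 16.7 points.

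**The case against.** Much can be said for the plan.

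- **A reader might infer that events are counted twice. They are not.** The final SAP presents Part B and Part A + B, with no Part A column. The overlap lies between an interim report already produced and the final report. The Part A rule also matches that report's own data cut.
- **A reader might infer that the primary endpoint is distorted.** The endpoint is the incidence and severity of TEAEs after multiple APL-2 doses. Every affected AE stays in Part A + B, so overall TEAE counts do not change.
- **A reader might infer that the imputation contradicts the SAP's conservative principle.** Section 4.4.1 defines that principle by the earliest on-treatment date, and the rule follows it literally. The gap is that neither section addresses study part.
- **A reader might assume that reactions are most likely on the first 1080 mg day.** The documents do not say so, and the point does not need it.
- **Subjects who switch after Visit 15 have no switch-day overlap**, and for them Part A is the correct home for Visit 15 AEs. The imputation gap still applies around their later switch date.
- **Few events may be involved.** Protocol section 14.4.1 asks for date and time of onset, transition visits follow at 1, 2 and 4 weeks, and unresolved dates are reviewed case by case with the original dates listed.

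All of this stands and limits the point. It does not remove the central gap: the case-by-case review has no criterion for study part, and the written rule sends uncertain events in one direction only.

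**Conclusion.** The point holds in a narrow form and is minor. In the Part B SAP, a post-switch AE leaves the Part B tables and Part B EAI if its start date is fully missing, lacks the day in the switch month (unless the switch is on the 1st), or lacks the month in the switch year (unless the switch is on 1 January). Partial dates in other months or years keep the correct part. Part A + B is unaffected.

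For subjects whose first 1080 mg dose is at Visit 15, the interim Part A report and the final Part B columns overlap on that one day.

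The size of the effect cannot be stated, because the documents give neither the number of partial-date AEs nor the number of subjects in Part B. The date shares above rest on first doses spread evenly over a year and a switch exactly on Day 336. The direction does not rest on those assumptions.

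**What to change.** Make the change in the Part B SAP. The Part A SAP has already been used and need not be reopened.

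1. For Part B assignment only: if a missing or partial start date is compatible with onset on or after the first 1080 mg dose, and the stop date is not before that dose, impute the first 1080 mg dose date. In the worked example the day-missing AE moves from 1 February to 13 February 2019, Part B Study Day 1.
2. Flag these AEs, and show Part B counts and EAI with and without them.
3. Assign AEs on the first 1080 mg date by recorded onset time relative to that dose; if the time is unknown, assign to Part B.
4. State in the final report which AEs were also counted in the interim Part A report.

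The cost is a short passage of SAP text, some programming and a few extra display rows. No new data are needed. The downside is real: some AEs that truly began in Part A may move to Part B. Each would then have a time to onset of one day (same date, plus 1), which raises the Part B EAI somewhat. The with-and-without display in step 2 shows by how much.

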## Adverse Events of Special Interest

Adverse events of special interest (AESI) include the following:

- Haemolysis / Haemolytic Anaemia
- Infection
- Thrombosis
- Hypersensitivity
- Clinically Significant Decrease in kidney function
- Injection Site reactions

AESIs will be determined by a review of all AEs by the clinical and data management study staff. This review will allow for the inclusion of AEs of special interest arising during the study that are not on the above list, based on a clinical decision. It is expected that documentation of the AEs of special interest will be maintained outside the Medrio database system by the biostatistics and data management staff (with review by medical) and used by the programmer for analysis of the AEs of special interest.

## Adverse Events Summary

An AE data listing of all AEs collected on study, including verbatim term, preferred term, treatment, severity, and relationship to treatment will be provided. Serious Adverse Events (SAEs), adverse events of special interest, and details of subjects withdrawing due to adverse events will also be listed. The start day (relative to the first dosing day), and the duration of AEs will be included in listings.

A topline summary for Part A, Part B, and Overall will present the number of events and the number of subjects by randomized dose level and by cohort with:

- any TEAE
- any TEAE considered as related to study drug (evaluated by the investigator as Unlikely Related, Unrelated, Possibly Related, Probably Related, Definitely Related, or Unknown)
- any serious TEAE
- Maximum severity TEAE of mild, moderate, severe, life threatening, and death; i.e. a subject with TEAEs at different intensities will be summarized at the most severe intensity
- any TEAE of special interest
- any TEAE leading to study drug discontinuation
- any TEAE leading to death

The table will also include the total number of TEAEs reported in each cohort and overall. The total number of unique terms within subjects will also be presented, counting each TEAE only once within each subject.

Additionally, the following will be tabulated with the number of events and the number/percent of subjects by randomized dose level in each cohort, and by cohort. Summaries will be ordered by descending order of event count in the overall column. All summary tables will be presented by study part and over the whole study, where AEs will be categorized by the Part in which the AE started i.e. an AE which began during the Part A Core Study Phase will be categorized under Part A even if it continues into Part B (unless it increases in severity).

- TEAEs by SOC and preferred term
- TEAEs by preferred term

• TEAEs regarded as at least possibly related to study drug by SOC and preferred term

The following will also be tabulated with the number/percent of subjects by randomized dose level in each cohort and by cohort:

- TEAEs and Serious AEs by SOC, preferred term, and maximum severity
- TE AESIs by SOC, preferred term, and maximum severity if applicable
- TE AESIs (regarded as at least possibly related to study drug) by SOC, preferred term, and maximum severity

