## 14.4.1 Relationship of Events to Study Treatment

All AEs that occurred during this study will be recorded. The PI will review each event and assess its relationship to study drug treatment (definitely related, possibly related, unlikely related, not related, unknown). The date and time of onset, time relationship to drug dosing, duration, and outcome (recovered/resolved, recovered/resolved with sequelae, recovering/resolving, not recovered/not resolved, fatal, or unknown) of each event will be noted.

The following definitions should be considered when evaluating the relationship of AEs and SAEs to the study treatment:

Definitely Related	
 
Event or laboratory test abnormality, with plausible time relationship to drug intake
 
Cannot be explained by disease or other drugs
 
Response to withdrawal plausible (pharmacologically, pathologically)
 
Event definitive pharmacologically or phenomenologically (ie, an objective and specific medical disorder or a recognized pharmacological phenomenon)
 
Rechallenge satisfactory, if necessary
 
	
Possibly Related	Event or laboratory test abnormality, with reasonable time relationship to drug intake     Could also be explained by disease or other drugs     Information on drug withdrawal may be lacking or unclear	
Unlikely Related	
 
Event or laboratory test abnormality, with a time to drug intake that makes a relationship improbable (but not impossible)
 
Disease or other drugs provide plausible explanations
 
	
Not Related	
 
Event or laboratory test abnormality, is plausibly related to the participant's clinical state, underlying disease, or the study procedure/conditions
 
Time relationship to drug intake makes a relationship unreasonable
 
Other obvious causes for event or laboratory test abnormality exist
 
	
Unknown	
 
Report suggests an AE, however, cannot be judged at this time because information is insufficient or contradictory
 
More data for proper assessment is needed, or additional data is under examination
 
	

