#### 15.2.2.1 Adverse Events

Treatment emergent adverse events are defined as those AEs that develop or worsen after the first dose of study medication and up to 30 days beyond the last dose of study medication. The current version of MedDRA will be used to classify all AEs.

A by-subject TEAE data listing, including verbatim term, preferred term, treatment, severity, and investigator judgment of relationship to treatment, will be provided. The number of subjects reporting each preferred term within each system organ class will be tabulated by cohort and dose group. Tabulations will be produced for all TEAEs and for those considered potentially treatment related (causality to study drug is reported as possibly or probably, or where causality is not reported). The number of TEAEs will also be presented including both the total number of TEAEs and the total number of unique TEAEs (counting only unique terms within each subject).

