#### Safety Set / Intent-to-Treat (ITT) / Pharmacodynamic (PD) Set:

Safety Set will only include the subjects who roll over to Part B and receive at least one dose of 1080 mg APL-2.

ITT Set and PD Set will be identical to the Safety Set for this study.

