#### **Overall Summary Table**

An overall AE summary will present the number of events and the frequency of subjects by cohort and by study part (Cohort 1 wAIHA Part A + B / Cohort 1 wAIHA Part B / Cohort 2 CAD Part A + B / Cohort 2 CAD Part B) with the following categories:

- any TEAE
- any TEAE considered as least possibly related to study drug (evaluated by the investigator as Possibly Related, Probably Related, Definitely Related, or Unknown)
- any serious TEAE
- Maximum severity TEAE of mild, moderate, severe, life threatening, and death, i.e. a subject with TEAEs at different intensities will be summarized at the most severe intensity
- any TEAE of special interest
- any TEAE leading to study drug discontinuation
- any TEAE leading to death

The total number of unique terms within subjects will also be presented in each of the categories above, counting each TEAE PT only once within each subject. Additionally, the total number of unique terms within cohorts will be presented in each of the categories above, counting each TEAE PT only once within each cohort.

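### The Part A SAP's topline row for drug-related TEAEs lists every causality category, so as written it repeats the any-TEAE row

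*SAP*

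**What the plan says.** The Part A SAP (27 Apr 2020), section 5.2.1, Adverse Events Summary, plans a topline table of events and subjects by randomized dose level and cohort. One row is any TEAE. The next is "any TEAE considered as related to study drug (evaluated by the investigator as Unlikely Related, Unrelated, Possibly Related, Probably Related, Definitely Related, or Unknown".

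The same section then plans "TEAEs regarded as at least possibly related to study drug by SOC and preferred term", and a table of AESIs with the same threshold.

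Protocol 14.4.1 sets the scale the investigator uses: "assess its relationship to study drug treatment (definitely related, possibly related, unlikely related, not related, unknown". Protocol 15.2.2.1 limits the treatment-related tabulations to TEAEs where "causality to study drug is reported as possibly or probably, or where causality is not reported".

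The Part B SAP (8 Nov 2022), section 5.2.1.6, Overall Summary Table, has the matching row. There it is worded as at least possibly related, and its parenthesis reads "evaluated by the investigator as Possibly Related, Probably Related, Definitely Related, or Unknown".

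**The concern.** A row headed as related TEAEs should separate events attributed to the drug from the rest. The Part A list includes the two categories that mean the opposite, so the stated rule excludes nothing that an investigator can record. A programmer who follows it would produce a second any-TEAE row under a relatedness label. That row would disagree with the related-TEAE tables later in the same report wherever any event was rated unlikely or not related.

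The error can only overstate. It sits in the summary that readers see first, and in the Part A report that summary is where the two randomized doses are set side by side at topline level.

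Two features of the plan keep it from correcting itself:

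- **Precedence.** Section 2 of the Part A SAP gives the SAP priority over the protocol's statistical section where they differ, so the narrower rule in Protocol 15.2.2.1 does not override the list.
- **No replacement in Part B.** The Part B SAP states that "Safety Set will only include the subjects who roll over to Part B and receive at least one dose of 1080 mg APL-2", and it tabulates by cohort and study part, not by randomized dose. Subjects who stopped during Part A are outside that set.

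**Working it through.** The plan gives no figure to reproduce here. The check is a comparison of category sets, followed by an illustration of size.

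**Step 1: compare the lists.** The reference is the five-category scale in Protocol 14.4.1: "definitely related, possibly related, unlikely related, not related, unknown". Unrelated in the SAP is read as the protocol's not related.

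| Protocol 14.4.1 category | In Part A SAP topline list | In Part B SAP topline list |
|---|---|---|
| Definitely related | yes | yes |
| Possibly related | yes | yes |
| Unlikely related | yes | no |
| Not related | yes (as Unrelated) | no |
| Unknown | yes | yes |
| **Covered** | **5 of 5** | **3 of 5** |

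Both SAP lists also name Probably Related, which is not on the current scale. The protocol's Amendment 4 summary of changes shows it in the superseded scale, so it matters only if older ratings remain in the database.

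**Step 2: consequence.** The protocol scale minus the Part A list is the empty set. Every TEAE with a recorded causality therefore falls in the row, and its event and subject counts equal those of the any-TEAE row. The only possible exception is a TEAE with causality left blank, which the list does not name. With the Part B list, the row excludes two categories and becomes a proper subset of any TEAE whenever an event is rated unlikely or not related.

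**Step 3: illustrative size.** The documents give no causality split and no TEAE count per subject, so both are assumed. Let *s* be the share of TEAEs that are truly in the related set and *k* the number of TEAEs per subject, the same for all subjects, with causality independent between events.

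- Event overstatement = 1/*s*.
- Subject overstatement = 1/(1 − (1 − *s*)^*k*).

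| *s* | Events | Subjects, *k* = 3 | Subjects, *k* = 5 | Subjects, *k* = 10 |
|---|---|---|---|---|
| 0.2 | 1/0.2 = 5.0 | 1/0.488 = 2.05 | 1/0.672 = 1.49 | 1/0.893 = 1.12 |
| 0.5 | 1/0.5 = 2.0 | 1/0.875 = 1.14 | 1/0.969 = 1.03 | 1/0.999 = 1.00 |

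The event count is distorted more than the subject count. The subject distortion fades as subjects accumulate events, because most subjects then have at least one related event in any case.

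**The case against.** The strongest reply is that the parenthesis was never an inclusion rule. Nobody would knowingly count unrelated events as related. The list may simply recite the response options or ask for a breakdown by category, as the severity row in the same list does when it names every grade. The Part B wording is later, and its head phrase changed as well as its list, so it is indirect evidence of what the 2020 text meant. A programmer may have applied the at-least-possibly-related threshold anyway, in which case no produced table is wrong.

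Part of this stands. Neither the shells nor the output was available, so it cannot be said that the produced row is wrong. The fold figures describe assumed cases, not this trial.

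The alternative reading does not rescue the text. The SAP does not say that a scale or a breakdown is meant. The severity row does announce its breakdown, by stating that each subject is counted at the worst grade. The Part B parenthesis has the same construction and makes sense only as a list of what counts. Even as a breakdown, the Part A text files unrelated events under related and sets no threshold, so it would still need correcting.

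The point about limited harm is fair. The study is descriptive, relatedness is not in the primary endpoint (incidence and severity of TEAEs), and the other related-TEAE tables and the full AE listing let a reader recover the right counts.

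**Conclusion.** The concern holds. As written, the Part A topline row for related TEAEs takes in five of five protocol causality categories and duplicates the any-TEAE row, except possibly for blank causality. It is inconsistent with the related-TEAE tables in its own section, with Protocol 15.2.2.1 and with the Part B SAP.

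The extent is one row of one table. The direction is certain, since the row cannot understate relative to the Part B definition for events with a recorded causality. The amount is unknown. The conclusion rests on reading the parenthesis as an inclusion list and Unrelated as not related. It should be fixed because it is a stated rule that gives a wrong safety count, even though no test, sample size or primary endpoint depends on it.

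The matter is not only prospective. The Part B SAP records that "Statistical Analysis Plan Version 1.0 was used for the production of the Interim Part A Core Study Phase Analysis", so a table built on this wording may already exist.

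**What to change.** 1. In Part A SAP 5.2.1, delete Unlikely Related and Unrelated from the row. It then counts Possibly, Probably (only if older ratings exist), Definitely and Unknown, as in Part B SAP 5.2.1.6.
2. Apply that same definition to the tables of at least possibly related TEAEs and AESIs. The Part A SAP does not currently say where Unknown falls in those tables.
3. Add one sentence to each SAP stating that missing causality counts as related, in line with Protocol 15.2.2.1. At present both SAPs leave missing safety data to case-by-case review and name only severity as an example.
4. Check the Part A topline table already produced, and correct the row if it followed the written list.
5. Optionally, add definitely related to the wording of Protocol 15.2.2.1 so that it matches the 14.4.1 scale. This changes no planned table, because both SAPs take precedence over that section.

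The cost is a one-line correction in the Part A SAP, one sentence in each SAP, and a check, with a re-run if needed, of one row. No new data are required.
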